### **3.7.3 Exploratory Endpoint Analyses**

#### Clinical and Laboratory Prognostic Factors

Exploratory analyses will be performed to identify the impact of clinical and laboratory prognostic factors on the primary endpoint or any secondary endpoint. Clinical factors include age, presence or absence of COPD, hypertension, or cardiovascular disease, or use of angiotensin converting enzyme inhibitors. Laboratory measurements including D-dimer, IL-6, LDH, ferritin, total WBC, absolute neutrophil count (ANC), absolute lymphocyte count (ALC), hemoglobin, hematocrit, platelet counts, and testosterone are measured during the patient's hospital stay. Further germline genomic factors will also be analyzed if feasible as prognostic factors for the study outcomes for part of the patients.

For continuous variables, the sample size, mean, SD, median, minimum, and maximum values for each treatment will be presented for each parameter at each data collection time point and tested using SAS PROC TTEST between the treatment groups. If a variable is not normally distributed the non-parametric method will be applied using SAS PROC NPAR1WAY (Table 3.7.3.1). For categorical variables, the number and percentage of participants by the treatment group will be tabulated and tested based on Pearson  $\chi^2$  test using SAS PROC FREQ (Table 3.7.3.2).

Univariate correlation with the primary endpoint or any categorical secondary endpoint will be assessed for each clinical and laboratory factor based on logistic regressions using SAS PROC LOGISTIC (Table 3.7.3.3). For the secondary endpoints of time to events data, univariate analysis will be performed based on Cox regressions using SAS PROC PHREG (Table 3.7.3.4). For the secondary endpoints of length of hospital stay and length of intubation for mechanical ventilation, nonparametric univariate analysis will be performed based on Spearman correlation method using SAS PROC CORR for the continuous prognostic factors, whereas Mann–Whitney U or Wilcoxon rank-sum test will be performed for the categorical prognostic factors using SAS PROC NPAR1WAY (Table 3.7.3.5). For those prognostic factors significantly associated with the primary and secondary outcomes from the univariate analyses, multiple regressions will be performed by adjusting some other prognostic factors identified from the univariate analyses. The multiple regressions will be performed as

described in the primary analysis and each corresponding secondary endpoint analysis (Table 3.7.3.6).

*Viral Load, Cytokines Levels, and TMPRSS2 Expression*

To explore the mechanisms that underlie treatment effect, nasopharyngeal (NP) epithelial or peripheral blood mononuclear cell (PBMC) TMPRSS2 expression, NP and plasma viral load, or serum cytokine (TNF- $\alpha$ , IL-1 $\beta$ , IL-6) levels will be tested among the participants from the Great Los Angeles site only.

Viral load kinetics in the two treatment groups over participants' critical period will be monitored from baseline to day 30. The viral load in plasma will be assessed by the viral RNA measured by a reverse-transcriptase–polymerase chain–reaction (RT-PCR) assay and quantified as  $\log_{10}$  copies/ml. Mean change from baseline in SARS-CoV-2 viral RNA load across each sample collection time point will be compared by the treatment groups. The mean value for  $\log_{10}$  copies/ml for each week will be calculated and summarized.  $\log_{10}$  copies/ml changes from baseline to each week will be summarized. For each week, the sample size, mean, SD, median, minimum, and maximum values for each treatment will be presented. A mixed-effect model of repeated measure (MMRM) for overall changes across all the time point between the two treatment groups using SAS PROC MIXED (Table 3.7.3.7). A longitudinal graph of  $\log_{10}$  copies/ml will be created and presented by 95% confidence intervals of the means (Figure 3.7.3.1).

Serum cytokines TNF- $\alpha$ , IL-1 $\beta$ , and IL-6, as well as TMPRSS2 expression and antiviral antibodies will be tested by immunoassays. Mean change from baseline in the cytokine and TMPRSS2 levels, and antibody titers across each sample collection time point will be compared by the treatment groups. The mean value for each week will be calculated and summarized. Mean changes from baseline to each week will be summarized. For each week, the sample size, mean, SD, median, minimum, and maximum values for each treatment will be presented (Table 3.7.3.8). A mixed-effect model of repeated measure (MMRM) for overall changes across all the time point between the two treatment groups using SAS PROC MIXED. A longitudinal graph of each measurement level will be created and presented by 95% confidence intervals of

the means (Table 3.7.3.9). If a measurement level is not normally distributed, then a non-parametric method will be used as an alternative analysis approach.

The exploratory analyses will not be adjusted for multiplicity.

#### **3.7.4 Site Effect Analysis**

Site effect will be evaluated for four participating sites. Balances of the treatment of assignment and the primary and secondary outcomes will be assessed among the four sites (Table 3.7.4.1). If there are significant associations between the site and treatment assignment and a study outcome at significance level of 0.05 without multiplicity adjustment, the site effect will be adjusted in the corresponding the primary or any secondary outcome along with the other prognostic factors described in the primary and secondary analyses.

#### **3.7.5 Long Term Effect Analysis**

The long-term analysis will be based on the data collected by following the randomized participants up to 60 days after randomization, which will include mortality, readmission to hospital, and oxygen use.

For mortality analysis, the treatment effect will be analyzed initially with a Pearson  $\chi^2$  test (Table 3.7.5.1a) and then logistic regression will be performed using SAS PROC LOGISTIC by taking account of prognostic factors described in the primary endpoint analysis (Table 3.7.5.1b).

For hospital readmission rate analysis, the treatment effect will be analyzed initially with a Pearson  $\chi^2$  test (Table 3.7.5.2a) and then logistic regression will be performed using SAS PROC LOGISTIC by taking account of prognostic factors described in the primary endpoint analysis (Table 3.7.5.2b). Further, time to hospital readmission will also be analyzed based on survival analysis techniques using log-rank test and Kaplan-Meier curves (Figure 3.7.5.1) by PROC LIFETEST, and Cox regression model adjusted for the covariates as described in the secondary endpoint analyses (Tables 3.7.5.3a-b).

For the oxygen use analysis, Pearson  $\chi^2$  test will be performed for this categorical endpoint using SAS PROC FREQ initially. Given the endpoint is also an ordinal variable, Cochran-Armitage test will be performed to test the ordinal trend

tendency using SAS PROC FREQ (Table 3.7.5.4a). in addition to the frequency analysis, proportional odds logistic regression will also be performed (Table 3.7.5.4b) using SAS PROC LOGISTIC by taking account of the factors of age, hypertension, COPD, and the baseline influenza scale (see Appendix 5.1).

The long-term analyses will not be adjusted for multiplicity.

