All patients should commence assigned treatment as soon as possible and no later than 48 hours (2 calendar days) after randomization.

Stratification Factors

Patients will be stratified according to 3 factors:

- Age: <65 vs. ≥65
- History of hypertension prior to hospitalization: yes vs. no

- Influenza severity scale: 3 vs 4/5

Study site is not a stratification factor because the participating sites will be in close communication to minimize variability in providing BSC. Other potential factors that can influence clinical outcome include COPD, asthma, and cardiovascular disease will be assessed for their relationship to clinical outcome in exploratory analyses.

Blinding

This is a randomized, double-blind study. Patient treatment assignments will remain blinded. The study biostatisticians and clinical research pharmacist may access treatment assignment information as necessary.

The investigational drug blind will be maintained using the IWRS. The drug and placebo injections will be dispensed by the research pharmacy and packaged to be made indiscernible from one another. To maintain the blind, the IWRS will ensure the investigator or designee is unaware of the treatment arm assigned to the subject. Prior to dispensing the study medications, the research pharmacist will verify the appropriate treatment arm assignment using the IWRS cross-referencing the patient's randomization number. The study drug will be delivered to an unblinded administrator of the study drug who is not part of the study team and who will not disclose information regarding study drug administration to any member of the study team, the patient or anyone else.

Unblinding Procedure

The CSPCRPCC will not provide Emergency Code Envelopes to the Research Pharmacy for HITCH. Emergency unblinding will be managed through the 24-hour emergency call service [contact]). This number is also listed on the patient ID cards given to each patient participating in HITCH. The system managed by the CSPCRPCC will electronically capture up-to-date study drug assignment information gathered from the HITCH IWRS.

Authorization to Break the Blind

Under unusual circumstances, chiefly related to patient safety and emergency medical necessity, unblinding may be necessary if knowledge of the study treatment assignment will influence the medical treatment of the patient. This is usually done after consultation with the Study Chair.

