### **3.5.2 Baseline Characteristics**

Baseline comparability among the treatment groups will be evaluated by providing a summary of baseline test results (D-dimer, IL-6, LDH, ferritin, total WBC, absolute neutrophil count (ANC), absolute lymphocyte count (ALC), hemoglobin, hematocrit, platelet counts, and testosterone) and baseline medical status (fever, oxygen needs, and days symptoms started prior to hospitalization) (Tables 3.5.2).

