### **3.5.3 Medical History**

The number and percentage of participants reporting a medical history will be summarized by the following medical conditions: COPD, hypertension, cardiovascular disease, asthma, diabetes, use of angiotensin converting enzyme inhibitors within last 30 days prior to hospitalization, and use of supplemental oxygen prior to hospitalization (Tables 3.5.3).

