## **3.6 Concomitant Medications**

Summaries for prior and concomitant medications will be done for the ITT population. Concomitant medications will be reported at screening, day 8,15,22, and 30. Each summary below will be done for each treatment group and for all participants:

- Prior medications – medications taken prior to the study drug administration
- Concomitant medications –medications taken on or after the study drug administration

All medications recorded on the CRF will be coded to the therapeutic drug classes and generic drug names using the World Health Organization (WHO) drug classifications. The current version of the WHO drug dictionary will be used for the coding of medications.

The number and percentage of participants who take medications that are coded to each generic drug name and therapeutic drug class will be tabulated by the treatment group and tested based on Pearson  $\chi^2$  test using SAS PROC FREQ (Tables 3.6.1-2). If there are significant differences between the two treatment groups for certain study related drugs, these concomitant medication use will be adjusted for the endpoint efficacy analyses when it is necessary.

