### **APPENDIX 5.1 7-category Ordinal Scale of Clinical Status of Hospitalized Influenza Patients**

- 1: Not hospitalized with resumption of normal activities.
- 2: Not hospitalized, but unable to resume normal activities,
- 3: Hospitalization, not requiring supplemental oxygen.
- 4: Hospitalization, requiring supplemental oxygen.
- 5: Hospitalization, requiring nasal high-flow oxygen therapy and/or noninvasive mechanical ventilation.
- 6: Hospitalization, requiring extracorporeal membrane oxygenation and/or invasive mechanical ventilation.
- 7: Death.

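### The oxygen-use analysis in SAP 3.7.5 leaves out oxygen use before admission, already collected and the closest baseline value of that outcome, at a modest cost in precision

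*SAP*

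**What the plan says.** SAP 3.7.5 adds a long-term analysis of data to 60 days after randomisation, "which will include mortality, readmission to hospital, and oxygen use". Oxygen use is described as ordinal. It gets a Pearson test, a Cochran-Armitage trend test, and a proportional odds model fitted "by taking account of the factors of age, hypertension, COPD, and the baseline influenza scale". The section makes no multiplicity adjustment.

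SAP 3.5.3 lists "use of supplemental oxygen prior to hospitalization" among the medical history items, but only for summary by arm. Neither document uses it as a covariate, a stratum, an exclusion criterion or a named exploratory prognostic factor.

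Three other passages come close without supplying the adjustment:
- SAP 3.5.2 summarises "baseline medical status (fever, oxygen needs, and days symptoms started prior to hospitalization"). This describes the patient at baseline, not before he fell ill.
- The protocol's stratification factors (section 4) include "Influenza severity scale: 3 vs 4/5", which is in-hospital status.
- SAP 3.6 says of drugs that differ significantly between arms that "these concomitant medication use will be adjusted for the endpoint efficacy analyses when it is necessary". The rule covers concomitant medications, not medical history.

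**The concern.** When an outcome has a recorded baseline value, that value is usually its strongest predictor, and adjusting for it is the standard way to gain precision. The SAP follows this logic for maximum severity in 3.7.2, where the model includes the baseline influenza scale. The same covariate list reappears for oxygen use in 3.7.5, but there the matching baseline is oxygen use before admission, and it was not added.

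The existing covariates cover it only partly. Level 4 of the scale in SAP Appendix 5.1 is "Hospitalization, requiring supplemental oxygen", which puts a man who already used oxygen together with one who newly needs it. COPD is associated with prior oxygen use but is not the same thing.

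Men on oxygen before admission who remain on it add events that treatment is unlikely to change. That shrinks the observed contrast, and a chance difference between arms in their number moves the estimate. The table would also not show how much of the oxygen use at follow-up is new.

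**Working it through.** **The plan's own figure.** The documents give no rate, power or sample size for Day 60 oxygen use. The only design figure is for the Day 15 composite (60% v 35%, 2:1, two-sided 0.05, 90% power). With pooled rate (0.60 + 2×0.35)/3 = 0.433, the control arm needs [1.96·√(1.5×0.433×0.567) + 1.2816·√(0.60×0.40 + 0.35×0.65/2)]² / 0.25² = 61, so 183 in total against 186 stated; power at 62 v 124 is 90.5%. The figure reproduces, but nothing below depends on it.

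**Step 1: dilution, unadjusted test.** Assumptions, none from the documents: a share h used oxygen before admission and all of them are on it at follow-up; among the others 30% (placebo) v 15% (degarelix) are on oxygen; all 66 v 132 are assessed. Arm rates are h + (1−h)×0.30 and h + (1−h)×0.15. At h = 10% these are 0.370 and 0.235, so the odds ratio is (0.235/0.765)/(0.370/0.630) = 0.52.

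| h | Risk difference (points) | Odds ratio | Power |
|---|---|---|---|
| 0 | 15.0 | 0.41 | 0.69 |
| 2% | 14.7 | 0.44 | 0.65 |
| 5% | 14.2 | 0.47 | 0.60 |
| 10% | 13.5 | 0.52 | 0.51 |

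**Step 2: chance imbalance.** The SD of the between-arm difference in prior use is √[h(1−h)(1/132 + 1/66)]: 3.3 points at 5% and 4.5 points at 10%. In the Step 1 setting a prior user's risk exceeds that of the others (average (0.30 + 2×0.15)/3 = 0.20) by 0.80. A one-SD imbalance at 10% therefore moves the risk difference by about 4.5×0.80 = 3.6 points.

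**Step 3: the planned type of model, with and without the term.** Step 1 overstates what is recoverable, because the planned model already holds COPD and the scale. Two simulations included both. Shared assumptions: binary outcome; 115 v 55 assessed; 15% (degarelix) v 32% (placebo) on oxygen among men not on it before; 90% among prior users; COPD in 60% of prior users and 15% of others; all prior users at level 4 or 5. Set A puts 65% of the others at level 4 or 5, with an odds ratio of 3 for that level. Set B puts 60% there, with odds ratios of 4 for the scale and 2 for COPD.

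| Prior users | Set A: planned → with term | Set B: planned → with term |
|---|---|---|
| 2% | 67% → 68% | 68% → 68% |
| 5% | 64% → 68% | 61% → 66% |
| 10% | 59% → 65% | 60% → 65% |

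The gain is 0 to 1 points at 2% and 4 to 6 points at 5% to 10%. In Set A at 10% the median odds ratio goes from 0.44 to 0.38.

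**Step 4: sparse cells.** With 170 men assessed, 5% prevalence means 170×0.05 = 8.5 prior users, of whom 55×0.05 = 2.75 are on placebo. If each has a 90% chance of being on oxygen at follow-up, the chance that there is at least one prior user and all are on oxygen is (1 − 0.1h)^170 − (1 − h)^170: about 0.43 at h = 5% and 0.68 at h = 2%. The coefficient for prior oxygen then has no finite maximum likelihood estimate, although the treatment coefficient can still be estimated.

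**The case against.** The strongest reply is that this is an extra SAP analysis. Oxygen use is not a protocol endpoint or one of the outcome variables in SAP 2.4, it has no multiplicity control, and the model already carries two related covariates. All of that stands, and it limits the point to a refinement.

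A reader might go further than the documents allow in four ways:
- **Bias.** One might infer that leaving the term out biases the comparison or inflates type I error. It does not. Under randomisation the planned tests remain valid and their p-values already allow for chance imbalance. Part of the odds-ratio shift is also the difference between a marginal and a conditional odds ratio.
- **Long-term home oxygen.** The item is any supplemental oxygen before admission. It may include short-term use in the days before hospital, and a man who used oxygen only at night might be scored level 3 on the scale.
- **Counted as COVID-19 failures.** SAP 3.7.5 does not define the oxygen-use categories, and the content of the post-discharge form is not in the documents. Coding relative to pre-admission use is neither shown nor ruled out. Those categories need defining whatever is decided about the covariate.
- **A larger power loss.** Leaving the scale out of the simulated model gives bigger gains (with COPD only, 0.60 to 0.67 at 5% and 0.50 to 0.60 at 10%, in the 30% v 15% setting with 95% of prior users still on oxygen). That is not the planned model. Nothing in the documents supports a prevalence of 15% or 20%.

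The objection that the term can fail to converge is also sound. SAP 3.7 refers convergence problems to 3.7.1, which gives no remedy for separation.

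**Conclusion.** The omission is clear from the text: the variable is collected in SAP 3.5.3, is absent from the analyses in 3.7.5, and no other section brings it in. The consequence is lost precision, attenuation, and an estimate exposed to chance imbalance. Randomisation protects the comparison, and no primary or secondary conclusion changes.

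The size is modest and uncertain. It rests on an assumed share of prior users, assumed Day 60 rates, an assumed strength for the existing covariates, and an outcome simplified to yes/no. If about 2% of men used oxygen beforehand, the gain is negligible. At 5% to 10% it is 4 to 6 points of power, and the result is easier to interpret because new oxygen use can be told apart from prior use. This is a low-cost improvement to a supplementary analysis, worth specifying before any data are analysed so that it is not a post hoc choice.

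**What to change.** In SAP 3.7.5:
- Add supplemental oxygen use before hospitalisation (yes/no) to the proportional odds model for oxygen use.
- Tabulate by arm oxygen use at follow-up among men who were not on oxygen before admission.
- Name in advance what happens if the new term separates, for example Firth penalised likelihood or an analysis restricted to men not on oxygen before admission.
- State the ordinal categories of oxygen use and the time point analysed.

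A Cochran-Mantel-Haenszel test stratified by prior oxygen is optional and adds little if that stratum is nearly empty.

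The cost is one covariate, one table row and a few sentences; no new data are needed. The drawback is the risk of sparse cells shown above, which the pre-specified remedy handles.

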### 3.8 Safety Analyses

All safety analyses will be done for the safety population and reported in tabular forms. These analyses include serious adverse events (SAE), study related to adverse events (AE), and AE with special interests to monitor drug toxicity.

#### 3.8.1 AE and SAE analyses

Adverse events (AE) and serious adverse events (SAEs) are defined by the ICH for Clinical Safety Data Management (ICH-E2A), the Food and Drug administration as described in the section 9. Incidence of AE/SAEs will be summarized for each treatment group by body system and MedDRA term. The number and percentage of participants with each body system and MedDRA term will be presented for each group. Pearson  $\chi^2$  test and/or Fisher Exact test were used to compare the frequency difference of AE and SAE between the treatment groups in System of Body (SOC) and Preferred Terms (PT) levels. Tables to summarize the incidence rates will be created for each of the following groups: Total AE and SAE, AE and SAE by relationship to study treatment, AE and SAE leading to premature discontinuation, AE and SAE presented in descending order of frequency by MedDRA term (no body systems shown). AE and SAE that led to premature discontinuation from the study will be listed. These listings will contain details about the SAEs such as outcome and relationship to study treatments. Other supportive data, such as the participant's age, will be given. All AE and SAE will be coded with MedDRA (updated version) and listed by participant. Tables to summarize the incidence rates will be created for each of the following groups:

- AE and SAE (Table 3.8.1a-b)
- AE and SAE by relationship to study treatment (Tables 3.8.2a-b)

- AE and SAE leading to premature discontinuation (Table 3.8.3a-b)
- AE and SAE presented in descending order of frequency by MedDRA term (no body systems shown) (Table 3.8.4a-b)

AE and SAE that led to premature discontinuation from the study will be listed.

These listings will contain details about the AE/SAEs such as outcome and relationship to study treatment. Other supportive data, such as the participant's age, will be given. All AE/SAEs will be coded with MedDRA (updated version) and listed by subject (Table 3.8.5).

### 3.8.2. Drug Toxicity Analysis

The drug toxicity will be closely monitored and analyzed. Cardiac arrhythmia and thromboembolic complications are adverse events of special interest (grade 3 and above) that will be monitored closely and graded according to on CTCAE 5.0. Once the toxicity markers reach a threshold of 25%, a statistical analysis of the toxicity will be performed. The treatment difference will be analyzed initially with a Pearson  $\chi^2$  test using SAS PROC FREQ (Table 3.8.2.1) and logistic regression will also be performed using SAS PROC LOGISTIC by taking account of prognostic factors described in the primary endpoint analysis (Table 3.8.2.2). If the experimental (degarelix) group has a significant higher toxicity compared to the placebo group at an  $\alpha$ -level of 0.01, then results will be reported to the DMC for a recommendation for trial termination.

